### 3.7 Endpoints

#### Primary Endpoint

It shall be considered the conversion to Alzheimer's disease within 3.0 years after diagnosis of MCI, together with the assessment of the subjects remaining in a stable condition and of those showing a reversion to the normal cognitive profile. People with MCI who convert to other forms of dementia will be considered separately. The biomarker or a set of biomarkers will be evaluated which can predict the conversion to Alzheimer's disease with higher accuracy.

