## **2. OBJECTIVES OF THE STUDY**

Whereas scientific literature is always more abundant in contributions to the profiles of individual sensitivity and specificity biomarkers, much fewer studies have evaluated combinations of multiple markers on the same study population. Furthermore, to date no study has assessed and validated an organization model for screening large part of the population using combinations of biomarkers, in terms of feasibility of costs, distribution and operational feasibility. Indeed these are the key points that this Protocol seeks to address.

The primary aim is to identify a biomarker or a set of biomarkers able to predict with greater accuracy the conversion of MCI to Alzheimer's dementia after 2 or 3 years of follow-up. The secondary aim is to define an optimal organizational model, as regards transferability in clinical practice of the defined diagnostic path of the primary objective as well as sustainability costs, in order to identify patients eligible to prescription of antidementia drugs which are currently under experimentation by RCTs.

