### 3.10 Statistical Analysis

Statistical analysis will be carried out following three areas:

1. Preparation of contingency tables for each of the seven biomarkers (MMSE; FCSRT; CSF CSF tau and p-tau/ABeta; F)FDG-PET; ApoE4; EEG) and processing parameters of sensitivity, specificity, positive predictive value and negative predictive value and overall accuracy. We will also calculate the positive and negative likelihood ratios (LR). The related 95% CI for each of these parameters shall also be calculated. The results will be compared with the positive and negative LR values, which are considered the gold standard for the placing on the market of a diagnostic test. (Jaeschke R, Guyatt GH, Sackett DL 1994)(see below).

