**Table 6. Interpretation of likelihood ratios**

Likelihood ratio Positive	Likelihood ratio negative	Changes in probability of the condition	Results
> 10	< 0.1	Large	Conclusive
5–10	0.1–0.2	Moderate	Moderately useful
2–5	0.2–0.5	Small	Sometimes useful
< 2	> 0.5	Tiny	Rarely useful
1	1	No change at all	Not useful

*(\*)Modified from: The investigation and management of the small-for-gestational-age fetus Royal College Obstetricians and Gynecologists - RCOG Guideline No. 31 November 2002*

2. For the two biomarkers with the highest sensitivity value we will proceed with an assessment in parallel with a mode "OR". Please note that in this study we use biomarkers in parallel in order to improve the overall specificity with respect to the use of every single biomarker. This implies that the purpose of the study is to develop an organizational model capable of identifying those subjects with MCI with the highest risk of converting to Alzheimer's disease (low percentage of false negative). Consider this theoretical example ([http://www.quadernodiepidemiologia.it/epi/screen/tst\\_com.htm](http://www.quadernodiepidemiologia.it/epi/screen/tst_com.htm)) which will be replicated with data captured in this study. Contingency tables can be set up separately for each of the 2 tests to calculate their sensitivity and specificity.

Compared to using a single test, in the case of interpretation «OR» it is less likely to miss a person with MCI converting to Alzheimer's dementia. However, there will be a low percentage of false negative, i.e. of subjects with AD at the end of the study but with biomarker negative at baseline. With this mode we might get an increase in sensitivity at the expense of specificity. In the case of interpretation «AND», it is easier to miss subjects with MCI converting to Alzheimer's disease, but there is a lower probability that a person with MCI is classified as a subject that will convert to Alzheimer's disease. Specificity increases at the expense of sensitivity.

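### The primary endpoint asks for the biomarker or set with higher accuracy, but the protocol fixes no measure of accuracy, ranks markers only by sensitivity, and plans and powers no paired comparison between markers

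*Protocol*

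**What the plan says.** Section 2 states the aim comparatively: "The primary aim is to identify a biomarker or a set of biomarkers able to predict with greater accuracy the conversion of MCI". The primary endpoint in 3.7 repeats it: "The biomarker or a set of biomarkers will be evaluated which can predict the conversion to Alzheimer's disease with higher accuracy". Neither defines accuracy.

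Section 3.10 has three areas.

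- **Area 1** is "Preparation of contingency tables for each of the seven biomarkers", with "processing parameters of sensitivity, specificity, positive predictive value and negative predictive value and overall accuracy", plus LR+ and LR-, which makes seven parameters. On precision: "The related 95% CI for each of these parameters shall also be calculated". The benchmark is external: "The results will be compared with the positive and negative LR values" of Table 6.
- **Area 2** holds the only ranking rule: "For the two biomarkers with the highest sensitivity value we will proceed with an assessment in parallel", in OR mode.
- **Area 3** fits regression models to find the best pattern of variables. The final proposal then also weighs cost, availability and invasiveness.

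Under 3.5 every subject has all seven markers within 60 days of T0, so the marker data are paired within subject. Both sample-size approaches in 3.9 concern one marker at a time: its sensitivity against a fixed null, or converters against non-converters.

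**The concern.** A claim that one marker or set is more accurate needs a measure that defines accuracy and an estimate of the difference between candidates with its uncertainty. The protocol fixes neither.

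Overall accuracy is one of the seven listed parameters, yet selection in area 2 runs on sensitivity, which looks at converters only. The rule that chooses the pair can therefore work against the endpoint that the pair is meant to serve. Area 2 is also at odds with itself: it gives better specificity as the reason for parallel use, then says that OR mode raises sensitivity at the expense of specificity.

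Section 3.9 intends the result to support decisions on prescribing. If the measure is chosen after the data are seen, so in effect is the winner.

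**Working it through.** **Inputs.** Sensitivity and specificity come from section 1.2. Conversion of 40% is the planning value in 3.9, and 26.6% to 39% is the range 3.9 takes from its two source studies. The sample is 400. The synopsis treats 400 as fully evaluated, while 3.9 mentions about 20% drop-out, so I show 160 converters (40% of 400) and 128 (40% of 320). Correlations between markers are my assumption, because the protocol gives none.

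**1. The protocol's own figures.** An exact binomial calculation reproduces the first approach in 3.9: 155 converters and N = 388 (power 0.818, p 0.044), 31 and 78 (0.807, 0.048), 107 and 268 (0.819, 0.040). These are correct, but they test one marker against a fixed null and do not compare two markers.

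**2. Which marker leads, at p = 40%.** Accuracy = p × sens + (1 − p) × spec; LR+ = sens/(1 − spec); LR- = (1 − sens)/spec; PPV and NPV by Bayes' rule.

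| Marker | Sens | Spec | PPV | NPV | Accuracy | LR+ | LR- |
|---|---|---|---|---|---|---|---|
| EEG | **0.87** | 0.64 | 0.617 | **0.881** | 0.732 | 2.42 | **0.203** |
| FCSRT | 0.81 | 0.71 | 0.651 | 0.849 | **0.750** | 2.79 | 0.268 |
| CSF | 0.71 | 0.77 | 0.673 | 0.799 | 0.746 | 3.09 | 0.377 |
| MMSE | 0.57 | **0.86** | **0.731** | 0.750 | 0.744 | **4.07** | 0.500 |
| MRI | 0.60 | 0.75 | 0.615 | 0.738 | 0.690 | 2.40 | 0.533 |
| FDG-PET | 0.57 | 0.67 | 0.535 | 0.700 | 0.630 | 1.73 | 0.642 |
| APOE4 | 0.52 | 0.66 | 0.505 | 0.673 | 0.604 | 1.53 | 0.727 |

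Three markers lead. The Table 6 bands do not settle it: EEG, FCSRT and CSF all fall in LR+ 2–5 and LR- 0.2–0.5.

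**3. Dependence on conversion.** FCSRT overtakes MMSE on accuracy at p = 0.15/(0.15 + 0.24) = 38.5%, and EEG overtakes FCSRT at p = 0.07/(0.07 + 0.06) = 53.8%. At 26.6%, MMSE has 0.266 × 0.57 + 0.734 × 0.86 = 0.783 against FCSRT 0.737, and only EEG and MMSE lead.

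**4. The pair the rule would choose.** EEG and FCSRT have the highest sensitivities. With independence given outcome, in OR mode:

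- sensitivity = 1 − 0.13 × 0.19 = 0.975
- specificity = 0.64 × 0.71 = 0.454
- accuracy at 40% = 0.4 × 0.975 + 0.6 × 0.454 = 0.663, against 0.732 (EEG) and 0.750 (FCSRT) alone

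With a within-group phi correlation of 0.3 the pair has sensitivity 0.936, specificity 0.520 and accuracy 0.686. With 0.5 it has 0.909, 0.563 and 0.702. It stays below both single markers. For comparison, AND mode under independence gives sensitivity 0.87 × 0.81 = 0.705, specificity 1 − 0.36 × 0.29 = 0.896 and accuracy 0.819.

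**5. What point estimates can carry.** In simulated trials of 400 at 40% conversion with independent markers, the highest observed accuracy belongs to FCSRT in 37%, CSF in 28%, MMSE in 26% and EEG in 10%. The FCSRT–CSF difference is 0.4 points. Its paired 95% half-width, 1.96 × √[(s − d²)/400], with s the proportion of subjects on whom exactly one of the two is correct and d the difference, is 6.0 points when correctness is independent (s = 0.377) and 4.3 points at correlation 0.5.

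**6. Power of a paired contrast.** EEG 0.87 against FCSRT 0.81 in converters, McNemar, two-sided 5%: power = Φ{[√n × d − z√s]/√(s − d²)}, where s is now the proportion discordant. At phi = 0, s = 0.165 + 0.105 = 0.271 and d = 0.06.

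| Converters | phi 0 | phi 0.3 | phi 0.5 |
|---|---|---|---|
| 160 | 31% | 41% | 53% |
| 128 | 26% | 34% | 45% |
| needed for 80% | 588 | 416 | 300 |

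**The case against.** **More than tables.** A reader might infer that the plan offers nothing but separate per-marker tables and looks for a single winner. It does not say that: 3.10 also has the OR pair and the regression models, and the endpoint covers a set. This stands. However, the OR pair is chosen on another measure than the endpoint names, and the regression area states no criterion tied to accuracy and no contrast between markers.

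**Sensitivity may be the intended measure.** Section 3.9 chooses its planning markers by sensitivity and powers on it, and area 2 gives few false negatives as the purpose. So it is too strong to say that the plan has no ranking measure. If sensitivity is meant, the aim and endpoint should say so; as written they ask for accuracy.

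**No overlap rule.** A reader might infer that markers will be compared by whether their separate CIs overlap. The protocol only says that CIs will be calculated. A power loss computed against such a rule would criticise something the plan does not contain, and none is claimed here.

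**SAP detail.** The choice of test or multiplicity method can be left to a statistical analysis plan, which is not shown. The mismatch between endpoint and ranking rule is in the protocol itself.

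**Close values.** The three-leader picture holds only between about 38.5% and 53.8% conversion, and the accuracy gaps are tiny. Another summary need not help: Youden's index is 0.52 for FCSRT and 0.51 for EEG. This stands, and it is a reason to state the uncertainty of differences.

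**Conclusion.** The concern holds in this form: the endpoint asks for higher accuracy, no measure of it is fixed, the one ranking rule uses sensitivity, and no contrast between markers measured in the same subjects is planned or powered.

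On the protocol's values, three markers lead on different listed parameters at 40% conversion and two at 26.6%. Following the sensitivity rule gives an OR pair with accuracy 0.663 under independence (0.702 at an assumed correlation of 0.5), below either component.

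This rests on the section 1.2 values, some from small studies (EEG from 30 subjects), and on assumed correlations. The mismatch in wording depends on neither. It should be corrected, but it does not invalidate the data collection.

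**What to change.** Before the encrypted archive is opened:

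1. Name one deciding measure in 3.7 and 3.10, and use it to select the pair in area 2. Alternatively, reword the aim and endpoint to sensitivity. Label the other parameters descriptive.
2. Reconcile the two statements in area 2 about specificity.
3. Compare markers and sets by paired differences with CIs on the same subjects: McNemar for sensitivity or specificity, or a subject-level bootstrap of the chosen measure. State a limited number of contrasts and control multiplicity.
4. Report leaders that do not differ as not distinguished, and let cost, availability and invasiveness decide between them.

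The cost is wording and minor programming, with no new data. The downside is low power between close markers. With 160 converters, EEG against FCSRT at the strictest Holm step of six contrasts (α = 0.05/6, z = 2.64 in the formula above) has 12%, 18% and 27% power at phi 0, 0.3 and 0.5. For the wider gap of 0.81 against 0.71 in 155 converters, with an assumed latent-normal correlation of 0 to 0.5, power is about 54–70% unadjusted, 27–42% at the strictest of six steps and 16–27% at the strictest of 21. Few contrasts are therefore better than all pairs, and the honest result may be that no single marker is best.

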#### Secondary Endpoints

Evaluation of cost/benefit ratio of individual biomarker or combination of biomarkers compared to their accuracy to predict progression from MCI to AD and their financial sustainability, availability in the country and non-invasiveness for patients.

### 3.8 Safety aspects

All subjects included in the interventional non therapeutic clinical study will be evaluated for safety determined through the assessment of adverse events (AES), serious adverse events, evaluation of laboratory tests, physical examination and vital signs. All information on safety will be collected, analyzed and evaluated by the CC in compliance with regulatory obligations provided for protection of patients in the study. Adverse events, whether observed by staff in clinics, or reported spontaneously by the patient or caregiver, or in response to a request, shall be documented in patients' CRF. Adverse events detected upon performing diagnostic techniques are defined as any adverse event associated with the use of the technique, whether or not it is considered technique-related.

### 3.9 Sample size

In order to calculate the sample size of this study which aims at identifying with the greatest possible accuracy the biomarker or set of biomarkers which could predict conversion from MCI to Alzheimer's dementia, the biomarkers are used as screening tests and then for their level of the sensitivity and specificity. The following table shows the sensitivity value pairs of seven biomarkers that were proposed in this study on the basis of evaluation of the literature reported in section 1.2 of the introduction.

**Table 1. Pairs of sensitivity values of seven biomarkers included in the study. The table shows that one pair of biomarkers (in bold and with an asterisk) is the combination of values of the highest sensitivity, including the use of**

DFR (FCSRT) and EEG. These two biomarkers were therefore taken into account for the calculation of sample size. Tables 2 and 3 show the values of sensitivity, specificity and positive/negative predictive value of the two biomarkers.

	MMSE	CSF p-tau	(  F)FDG-PET	DFR (FCSRT)	APOE4	EEG	Volumetric MRI
MMSE							
CSF p-tau	57/71						
(  F)FDG-PET	57/57	71/57					
DFR (FCSRT)	57/81	71/81	57/81				
APOE4	57/52	71/52	57/52	81/52			
EEG	57/87	71/87	57/87	81/87*	52/87		
Volumetric MRI	57/60	71/60	57/60	81/60	52/60		

Table 2 Data included in Grande's paper et al. submitted

Giulia	AD					
follow-up 2.5 anni	1	0				
DFR	1	59	33	92	sens	0.81
	0	14	81	95	spec	0.71
		73	114	187	vpp	0.64
					vpn	0.85

Table 3 Poil's study et al. 2013 (follow-up of 2 year) (EEG)

Poli 2013	AD					
follow-up 2 anni	1	0				
EEG	1	7	8	15	sens	0.88
	0	1	14	15	spec	0.64
		8	22	30	vpp	0.47
					vpn	0.93

In 2 years of the follow-up the conversion rate from MCI to AD is 26.6% (8/30). In summary, after a follow-up of about 2.5 years, the prevalence of AD in a cohort of patients with MCI ranges from 26.6% to 39%. Based on these data, it was decided to adopt 2 approaches, one based on the methodological work of Bujang & Adnan (Requirements for Minimum Sample Size for Sensitivity and Specificity Analysis. J Clin Diagn Res. 2016 Oct; 10 (10): YE01-YE06), the other using the logic of a case control study, in which the cases are represented by patients converting to Alzheimer's disease, while the control is represented by patients with MCI. In the latter case an OR was

calculated between the biomarker and positive AD presence. In detail, the first approach allows us to predict a number of patients with MCI ranging from 78 to 388 in the hypothesis of a prevalence of 40% Alzheimer Dementia after 3 years of follow-up and a sensitivity value (working hypothesis) of 80-90% for an individual biomarker with a potency of about 81% and a p value lower than 5% (see below-from Bujang & Adnan 2016).

n (Sensitivity)						
Prev	H 0	H 1	Power	p-value	N1	N
40%	0.70	0.80	0.818	0.044	155	388
40%	0.70	0.90	0.807	0.048	31	78
40%	0.80	0.90	0.819	0.040	107	268

In detail, the second approach, typical of a case control study, has allowed to estimate with a power of 99% and a p value of 0.001 the following patients with MCI, depending on the type of biomarker. For the purposes of this study, it was decided to use very high values for alpha and beta parameters in order to minimize the statistical error of the first and second kind, thus giving priority to the use of the data for a decision at an individual level.

OpenEpi software was employed to calculate data in the tables 2 and 3. Tables 4 and 5 show details of sample size for two separate biomarkers by highlighting the value of OR between biomarker positivity and onset of Alzheimer's dementia.

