**Biomarker 5: at least the presence of one allele APOE ε 4**

Title meta-analysis of four prospective studies: “Apolipoprotein 4 allele ε4-as a significant risk factor for conversion from mild cognitive impairment to Alzheimer's disease: a meta-analysis of prospective studies (n = 458) (Fei M. et al. 2013)”.

	Fei 2013 n=458	n=400	n=600	n=800
Sensitivity (CI95%)	0.52 (0.45; 0.60)	0.52 (0.44; 0.60)	0.52 (0.46; 0.59)	0.52 (0.47; 0.58)
Specificity (CI95%)	0.66 (0.59; 0.71)	0.66 (0.59; 0.71)	0.66 (0.60; 0.70)	0.66 (0.61; 0.70)

Biomarker 6: multiple six electroencephalogram (EEG) biomarkers into a diagnostic classification index

It was identified the following study "Integrative EEG biomarkers predict progression to Alzheimer's disease at the MCI stage." (Poil SS et al., 2013), which shows interesting values of sensitivity and specificity of the EEG via modern methods of analysis.

	Poil n=30	n=400	n=600	n=800
Sensitivity (CI95%)	0.87 (0.47; 1.00)	0.87 (0.80; 0.93)	0.87 (0.81; 0.92)	0.87 (0.82; 0.91)
Specificity (CI95%)	0.64 (0.41; 0.83)	0.64 (0.58; 0.69)	0.64 (0.59; 0.68)	0.64 (0.60; 0.68)

Biomarker 7: volumetric MRI

Title pooled analysis: "Imaging markers for Alzheimer's disease: which vs how. Neurology 2013; 81:487-500, (Frisoni G.B. et al., 2013)".

	Frisoni 2013 (n=416)	n=400	n=600	n=800
Sensitivity (CI95%)	0.60 (0.51; 0.68)	0.60 (0.51; 0.68)	0.60 (0.54; 0.66)	0.60 (0.55; 0.65)
Specificity (CI95%)	0.75 (0.67; 0.82)	0.75 (0.67; 0.82)	0.75 (0.70; 0.79)	0.75 (0.71; 0.79)

**The present study protocol is focused on the second scenario and therefore includes the definition of prodromal AD (IWG2) or MCI (NIA-AA).**

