Where Var and Cov are variances and the covariance of the signals. This equation was developed as a measure of true physiological connectivity not affected by volume conduction and low spatial resolution. The values of lagged linear connectivity computed between all pairs of ROIs for each frequency band will be used as weights of the networks built in the graph analysis.

Graph analysis: a network is a mathematical representation of a real-world complex system. It is defined by a collection of nodes (vertices) and links (edges) between pairs of nodes. Nodes usually represent brain regions, while links represent anatomical, functional or effective connections, depending on the dataset. Anatomical connections typically correspond to white matter fiber tracts between pairs of grey matter brain regions (cortical areas or subcortical relays). Functional connections correspond to magnitudes of temporal correlations in activity and may occur between pairs of anatomically unconnected regions. A weighted graph is a mathematical representation of a set of elements (vertices) that may be linked through connections of variable weights (edges). Weighted and undirected networks will be built, the vertices of the network being the estimated cortical sources in the BAs, and the edges being weighted by the Lagged Linear value within each pair of vertices. The software instrument for the graph analysis will be the Brain Connectivity Toolbox (BCT, [brain-connectivity-toolbox.net](http://brain-connectivity-toolbox.net)), adapted with our own Matlab scripts.

The Small World (SW) parameter will be evaluated on brain networks, since it measures the balance between local connectedness and the global integration of a network, representing brain network organization. Small-world organization is intermediate between that of random networks, the short overall path length is associated with a low level of local clustering, and that of regular networks or lattices, the high-level of clustering of which is accompanied by a long path length. The measure of network small-worldness will be defined as the ratio of the normalized Clustering Coefficient  $C_w$  and the normalized Path Length  $L_w$ . To obtain individual normalized measures, the values of characteristic path length and of the clustering coefficient will be divided by the mean values obtained from the average values of each parameter in all frequency bands of each subject.

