**Table 4 Delayed Free Recall (DFR) (Free and Cued Selective Reminding Test -FCSRT)**

**Sample size dimensions for a case-control unpaired study**

---

For:

Level of bilateral confidence (1-alpha)	99.9
Potency (% possibilità di individuazione)	99
Ratio controls-cases	1
Hypothetical proportion of controls with exposure	29
Hypothetical proportion of cases with exposure	81
Minium Odds Ratio to identify:	10.44

---

	Kelsey	Fleiss	Fleiss con CC
Sample size – Cases	58	51	55
Sample size - Controls	58	51	55

---

Sample Size- total  
sample

116

102

110

---

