**Table 5. EEGSample size dimensions for a case-control unpaired study**

For:	Level of bilateral confidence (1-alpha)	99.9	
	Potency (% possibility of identification )	99	
	Ratio controls-cases	2	
	Hypothetical proprtion of controls with exposure	36.4	
	Hypothetical proprtion of cases with exposure:	87.5	
	Odds Ratio minimo estremo da rilevare:	12.23	
	Kelsey	Fleiss	Fleiss con CC
Sample size – Cases	46	38	41
Sample size - Controls	91	75	81
Sample Size- total sample:	137	113	122

It is not possible to apply an estimate of sample size to a pair of biomarkers as there are no specific data in the literature for the 2 couples with the highest sensitivity values previously reported (table 1). It should be noted that -as will be reported in the next paragraph- it is necessary to capture the full data set in order to have the number of cases which convert and do not convert to Alzheimer’s dementia for each of the 4 combinations of a biomarker pair (++; +-;+;- -). On the basis of relevant literature, using two specific approaches for sample size calculation for a single biomarker and estimating an approximate 20% drop-out rate for various reasons (death, severe neurodegenerative disease, dropout for poor compliance) during the follow up, a sample size of 400 patients with MCI is considered sufficient to highlight a biomarker or a pair of biomarkers with such a level of accuracy as to trigger the decision to prescribe a new anti-dementia medicinal product.

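### The 99% power at alpha 0.001 in section 3.9 is for detecting any association (odds ratio not 1), so it does not support the claims about individual decisions or prescribing-level accuracy

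*Protocol*

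**What the plan says.** Protocol section 3.9 sizes the study in two ways.

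- **First approach.** A one-sample test of sensitivity against 0.70 or 0.80, at 40% conversion, about 81% power and 5% alpha. It gives 78 to 388 patients.
- **Second approach.** An unpaired case-control calculation, which "has allowed to estimate with a power of 99% and a p value of 0.001 the following patients with MCI". Tables 4 (FCSRT) and 5 (EEG) list its inputs: "Level of bilateral confidence (1-alpha") of 99.9, power 99, the "Ratio controls-cases", the marker-positive proportions in controls and cases, and a minimum odds ratio to detect. Totals run from 102 to 137.

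The extreme alpha and power are justified as "thus giving priority to the use of the data for a decision at an individual level". Section 3.9 closes by citing both approaches and judging 400 patients enough to find a marker or pair "with such a level of accuracy as to trigger the decision to prescribe a new anti-dementia medicinal product".

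Section 3.10 does not judge markers by an odds-ratio test. It uses sensitivity, specificity, predictive values and likelihood ratios with 95% intervals, graded against Table 6.

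**The concern.** Alpha and power control the errors of one stated hypothesis test. If the null is no association, a very small alpha and very high power make a group-level association very likely to be declared correctly. They do not make the marker better at classifying a patient, and they do not show that it will be good enough to act on. Section 3.9 moves from one to the other, first in the clause about individual decisions and again in its closing sentence.

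At stake is how the result is read. The study is meant to inform who would be eligible for new drugs. A reader could take 99% power at 0.001 as an assurance about accuracy, when the part of the design that does test accuracy has about 81% power at 5%, for sensitivity alone.

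**Working it through.** **1. Reproduce Tables 4 and 5.** Inputs: two-sided alpha 0.001 (z = 3.2905) and power 99% (z = 2.3263), so (3.2905 + 2.3263)² = 31.55.

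Kelsey: cases = 31.55 × p̄(1 − p̄)(r + 1) / (r d²), where r is controls per case, d the difference in marker-positive proportions and p̄ their weighted mean.

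- FCSRT: 0.81 vs 0.29, r = 1, p̄ = 0.55, d = 0.52. 31.55 × 0.2475 × 2 / 0.2704 = 57.8; Table 4 has 58.
- EEG: 0.875 vs 0.364, r = 2, p̄ = 0.5343, d = 0.511. 31.55 × 0.2488 × 1.5 / 0.2611 = 45.1 cases and 90.2 controls; Table 5 has 46 and 91.

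The Fleiss figures also reproduce on rounding up: FCSRT 50.9 and, with continuity correction, 54.7 (printed 51, 55); EEG 37.1 and 40.0 cases, the latter just above 40 (printed 38, 41). All of these formulas have the null of equal proportions. Section 3.9 does not state the null in words, but the match fixes it as odds ratio = 1.

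**2. What passes that test with 400 evaluable.** Assume 40% conversion (the first approach's figure): 160 converters, 240 non-converters. Sensitivity and specificity are those in section 1.2. LR+ = sens / (1 − spec). PPV = 0.4 sens / [0.4 sens + 0.6 (1 − spec)]. Power is the normal two-proportion formula at two-sided 0.001.

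FDG-PET: 0.57 vs 0.33, pooled 0.426. Null SE = √(0.426 × 0.574 × (1/160 + 1/240)) = 0.0505. Alternative SE = √(0.57 × 0.43/160 + 0.33 × 0.67/240) = 0.0495. (0.24 − 3.2905 × 0.0505) / 0.0495 = 1.49, so power is 93%.

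| Marker | Sens/spec | LR+ | PPV at 40% | Power to reject OR = 1 at 0.001 |
|---|---|---|---|---|
| MMSE | 0.57/0.86 | 4.07 | 73% | >99.9% |
| FCSRT | 0.81/0.71 | 2.79 | 65% | >99.9% |
| CSF | 0.71/0.77 | 3.09 | 67% | >99.9% |
| FDG-PET | 0.57/0.67 | 1.73 | 54% | 93% |
| APOE4 | 0.52/0.66 | 1.53 | 50% | 62% |
| EEG | 0.87/0.64 | 2.42 | 62% | >99.9% |
| MRI | 0.60/0.75 | 2.40 | 62% | >99.9% |

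Table 6 puts LR+ below 2 in its rarely-useful band and 2 to 5 in its sometimes-useful band. FDG-PET is in the former and still passes the test with 93% power. The two sizing markers, FCSRT and EEG, are in the latter.

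**3. Power the design has for accuracy.** The first approach reproduces by exact binomial test: 155 converters, 0.70 vs 0.80, two-sided p 0.044, power 0.818, and 155/0.4 = 387.5, printed as 388. With 160 converters:

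| Sensitivity, null vs alternative | Two-sided 0.05 | Two-sided 0.001 |
|---|---|---|
| 0.70 vs 0.80 | 81% (reject at ≥124 of 160) | 32% (reject at ≥131 of 160) |
| 0.80 vs 0.90 | 92% | 46% |
| 0.70 vs 0.90 | >99.9% | 99.9% |

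So, except for the widest contrast, the strict error rates of the second approach do not carry over to sensitivity. Specificity, likelihood ratios and predictive values have no power calculation.

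**4. Precision for a likelihood ratio.** FCSRT with 160/240: ln 2.79 = 1.027. SE = √(0.19/(160 × 0.81) + 0.71/(240 × 0.29)) = √(0.00147 + 0.01020) = 0.108. The 95% CI is exp(1.027 ± 1.96 × 0.108) = 2.26 to 3.45.

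**The case against.** The strongest reply is that 400 does not come from this calculation. The second approach gives at most 137. The only figure near 400 is the first approach's 388, and that does test an accuracy measure. This stands. A reader might infer that 400 is unsupported or too small; the protocol does not bear that out, since 388 fits within 400 evaluable (the Synopsis plans about 480 enrolled for 400 fully evaluated).

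Second, a reader might say the protocol claims 99% power for individual decisions. It does not say so in those words. It gives 99% power for an odds-ratio calculation and offers individual decisions as the motive for the strict settings. The fault is narrower: the motive does not follow, and the closing sentence relies on it.

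Third, precision at n = 400 is largely there already. Section 1.2 tabulates 95% intervals for sensitivity and specificity, and section 3.10 commits to intervals for likelihood ratios. Only a planning likelihood-ratio interval would be new.

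Fourth, LR+ is not the whole of Table 6. EEG's LR− is 0.125/0.636 = 0.197 from Table 5's inputs, just inside the moderately-useful band; from 0.87/0.64 it is 0.203, just outside. FCSRT's is 0.19/0.71 = 0.27. Nor does every marker pass: APOE4 has 62% power. Both points qualify the picture without changing what the test shows.

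Finally, one could put the lower confidence limit of EEG sensitivity (0.47) into Table 5's Kelsey formula, obtain about 3,030 subjects instead of 137, and conclude that the size is badly wrong. That does not follow. It takes the extreme end of an interval from 8 converters and uses a formula that does not address accuracy. The match between the cited EEG index and this study's EEG measure is a separate question, not needed here.

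**Conclusion.** The point holds as a misstatement in section 3.9 of what the calculation shows, not as an error in the sample size. The arithmetic in Tables 4 and 5 is correct for rejecting odds ratio = 1. The stated 99% power at alpha 0.001 supports neither the individual-level clause nor the closing claim of accuracy sufficient to trigger prescribing.

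The size of the gap: a marker with LR+ 1.73 and PPV 54% would pass with 93% power, while power for the protocol's own accuracy contrast of 0.80 against 0.70 is about 81% at two-sided 5% and about 32% at two-sided 0.001.

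These figures assume 400 evaluable, 40% conversion and the section 1.2 accuracies. At the 26.6% conversion also quoted in section 3.9, 400 evaluable would give about 106 converters and about 63% power for 0.80 against 0.70 at two-sided 5%. If 400 were instead the enrolled number, 20% dropout would leave 320, or 128 converters at 40%, and power would be about 67%.

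**What to change.** In section 3.9:

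- Relabel the second approach and Tables 4 and 5 as power to detect any association between marker positivity and conversion.
- Remove the clause that ties the strict alpha and power to individual decisions.
- Restate the closing sentence so that 400 evaluable patients rest on the first approach: about 81% power, 5% alpha, sensitivity only (0.80 against 0.70), 40% conversion. Refer to the intervals already tabulated in section 1.2, and say plainly that 400 is the evaluable number.
- Add a planning likelihood-ratio interval, for example FCSRT LR+ 2.79, 95% CI 2.26 to 3.45 with 160 converters and 240 non-converters.

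The cost is rewording one section. Enrolment, data collection and the analyses in section 3.10 stay as they are. The downside is a less favourable stated power.
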